8 RESEARCH QUESTION AND OBJECTIVES

This PASS is an international, observational cohort study (registry) of pregnancy outcomes in women with MS exposed to LEMTRADA during pregnancy.

Pregnancy outcomes in women exposed to LEMTRADA will be compared with available data from external comparison groups: women with MS not exposed to LEMTRADA, and women without MS.

The overall goal of the registry is to compare maternal, fetal and infant outcomes in women exposed to LEMTRADA with the outcomes in women from unexposed external comparison groups during pregnancy and to assess if the risks of any adverse pregnancy outcomes and birth defects in women exposed to LEMTRADA during pregnancy exceeds the risks in women of unexposed external comparison groups. The registry will detect and record the following outcomes:

- Primary outcome:
 - Spontaneous abortion
- Secondary outcomes:
 - Major and minor congenital malformations;
 - Pregnancy outcome: stillbirth, elective terminations, preterm birth, full-term live birth;
 - Small for gestational age at birth;
 - Any other adverse pregnancy outcomes.

These outcomes will be assessed throughout pregnancy. Infant outcomes, including effects on postnatal growth and development, will be assessed through the first year of life.

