- a) Gender, gestational age at delivery, mode of delivery, type/length of hospital stay, maternal and neonatal complications, maternal weight gain, presence or absence of major and minor structural defects, Apgar scores, birth weight, birth length, and head circumference.
- For other outcomes.
- a) Gestational age at time of event, pathology results if available, and presence or absence of major and minor structural defects. For stillborn infants gender, birth size, and autopsy results.
- Safety data
 - All SAEs including medically important events (see Section 11.1.1 for details),
 - All non-serious adverse events which per opinion of HCP/National Coordinator potentially have an impact on pregnancy outcomes.

At the conclusion of the pregnancy outcome interview, upon local practice, when local legislation requires this in addition to ICF signature, women can be mailed a packet with medical records release forms (or equivalent) from the pre- and postnatal HCP, the delivery hospital, and the pediatrician. Women will be asked to sign the medical records release forms and return the signed forms to the HCP(s). This process is to allow the National Coordinator to contact HCPs to confirm pregnancy outcomes and other above described data.

For retrospective cases, all data collections described above are applicable except that there would be no trimester interviews because the pregnancy outcome is already known.

Targeted follow-up

If a birth defect is noted, additional details regarding the birth defect may be requested from HCP by NC or by BDE to further define the etiology, facilitate classification, and to assess the presence of potential confounders of the birth defects. In addition, any specific questions the BDE (see Section 9.4) might have following initial review of the case will be included on the Targeted Follow-up Form.

The Targeted Follow-up Form collects the following from the reporter of the birth defect(s) or other appropriate HCP:

- Additional details of the birth defect (from initial report)
 - Assessment of etiology from HCP perspective
 - Requirement of surgical intervention to treat the birth defect (if so, dates and details)
- Potentially contributory factors
 - Medications or other products or agents taken during pregnancy
 - Maternal and paternal occupation
 - Concurrent medical/clinical conditions (occurring prior to and/or during pregnancy)
 - Any other factors that might have contributed to this outcome

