9.7.5 Statistical methods

Endpoints are prospectively collected rates of spontaneous abortion, major and minor congenital malformations, stillbirth, elective terminations, preterm birth, small for gestational age at birth, and any other adverse pregnancy outcomes for women exposed to LEMTRADA during pregnancy.

All the comparisons below between women exposed to LEMTRADA during pregnancy (prospectively collected) and unexposed comparison groups will be carried out separately against each comparison group.

Rates and 95% CI will be calculated. Rates will be compared between women exposed to LEMTRADA during pregnancy (prospective) and women in unexposed comparison groups by calculating the relative risk (RR) and its 95% CIs. As the majority of the events rates are anticipated to be low, when applicable, comparisons will be conducted using exact statistical methods.

A supportive analysis of (prospective) spontaneous abortion as a time-to-event endpoint will be conducted using the Kaplan-Meier method adjusting for left-truncation. If data are available, propensity score matching and covariate adjustment may be used in the Cox regression context with left-truncation to adjust for potential confounding factors, such as gestational age at enrollment, comorbidities, prior birth defects/abnormalities, exposure to other medications, etc.

For other endpoints (prospective), if data are available, propensity score matching and covariate adjustment may also be used in the logistic regression context to adjust for potential confounding factors. These approaches will reduce the influence of risk modifiers in determining the event risk ratio between Lemtrada-exposed women and non-Lemtrada-exposed women.

Qualitative descriptive statistics on maternal and pregnancy characteristics and the timing of LEMTRADA exposure will be provided for the retrospectively collected pregnancy cases.

Additional supportive analyses will be documented in the statistical analysis plan (SAP).

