9.9 LIMITATIONS OF THE RESEARCH METHODS

As reporting of pregnancies is totally voluntary, it is possible that even in prospectively reported cases, potential bias could exist.

The primary limitation of an international, prospective observational cohort study is selection bias (12). Women who voluntarily enroll may represent particularly high or low risk pregnancies, leading to potential over- or under-ascertainment of potential malformations and adverse pregnancy outcomes such as spontaneous abortion. The impact of selection bias can be minimized through robust outreach to recruit women exposed to LEMTRADA during their pregnancy, and efforts to retain all women who enroll into the study through the entire study follow-up period. Outreach strategies will include dissemination of information about the study and how to enroll through a variety of venues. Another potential limitation is that the calculation of fetal malformations will exclude information from spontaneous abortions, induced abortions, or fetal deaths where information on malformations was not available. For these excluded fetal losses, it is unknown what percentage would have resulted in potentially normal outcomes or malformations, leading to potential over or underestimation of malformation rates. The use of unexposed external comparison groups will also address these limitations to some extent.

Pregnancy outcome information is considered "lost to follow-up" if unobtainable after 4 attempts. It is possible that outcomes among pregnancies lost to follow-up could differ from those with documented outcomes. Because of differences in follow-up procedures across countries and individual reporting patterns, it is currently not possible to assess with any certainty what impact the potential biases the losses to follow-up may have on the analysis. However, efforts at comparing some of the characteristics of each group may be conducted in an attempt to address this potential source of bias.

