14 APPENDICES

Appendix A Description of pregnancy outcomes

Each defect will be categorized using the CDC MACDP classification of birth defects (CDC MACDP, 1998). Major defects identified from the point of conception up to 1 year of age will be included in the analysis. Defects identified in any live birth will be considered in the primary analysis. Defects identified in any stillbirths or abortions (spontaneous or induced) will be considered in secondary analyses.

MACDP defines major structural or genetic birth defects as conditions that

- 1. result from a malformation, deformation, or disruption in one or more parts of the body, a chromosomal abnormality, or a known clinical syndrome;
- 2. are present at birth;
- 3. have a serious, adverse effect on health, development, or functional ability.

A **minor** structural defect is defined as a defect which occurs in less than 4 percent of the population but which has neither cosmetic nor functional significance to the child (e.g., complete 2,3 syndactyly of the toes).

Spontaneous abortion

Any loss of a fetus due to natural causes at \leq 20 weeks gestation determined from the estimated date of conception or by ultrasound as spontaneous abortion. If available, information from gross or pathological examination of the abortus or fetus will be documented.

Induced abortion

Pregnancy termination is defined as any induced or voluntary fetal loss. If available, information from gross or pathological examinations will be documented.

Preterm birth

A live birth that occurs before 37 completed weeks of gestation determined from the estimated date of conception. Elective caesarian deliveries or inductions prior to 37 completed weeks will be analyzed separately.

Small for gestational age

Birth size (weight, length, or head circumference) ≤10th percentile for gender and gestational age using the NCHS pediatric growth curves for full term infants. Prenatal growth curves will be used for preterm infants.

Property of the Sanofi Group - strictly confidential

Stillbirth

Any non-deliberate foetal death at >20 weeks gestation as estimated based on the estimated date of conception or by ultrasound.

Lost to follow-up

Enrolled women will be considered lost to follow-up if they are eligible, have provided informed consent, and have completed the initial intake interview but pregnancy outcome information is not available within 1 year of the estimated delivery date despite 4 attempts to obtain this information.

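### Small for gestational age counts any one of three birth measures, so its rate, and the relative risk, depends on how many measures are recorded

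*Protocol*

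**What the plan says.** Protocol section 8 lists "Small for gestational age at birth" as one secondary outcome. Appendix A defines it as "Birth size (weight, length, or head circumference) ≤10th percentile for gender and gestational age using the NCHS pediatric growth curves for full term infants", and adds: "Prenatal growth curves will be used for preterm infants". Preterm is defined in the same appendix as "A live birth that occurs before 37 completed weeks of gestation determined from the estimated date of conception". The SGA definition does not name a deciding measure or require a minimum number of measures.

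For exposed live births, section 9.6.2.1 collects "Apgar scores, birth weight, birth length, and head circumference" as separate items, together with gender and gestational age at delivery. Section 9.6.2.2 has health care providers verify the same items.

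Section 9.7.5 compares the rate of each endpoint, SGA included, with each unexposed group separately, by a relative risk and its 95% confidence interval. Section 9.7.4.3 promises de-identified patient-level data from Cohorts II and III of the teriflunomide registry. The variables it then lists include no birth weight, length or head circumference.

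**The concern.** A rule satisfied by any of three correlated measures gives each infant up to three chances to be classified. An infant with only a birth weight has one chance. The SGA rate of a group therefore rises with the completeness of its length and head-circumference records, even when growth is the same.

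This matters because the two sides of the comparison are gathered differently. The exposed group comes through many health care providers in North America, Europe and the rest of the world. Cohorts II and III come from one North American registry. If recording is less complete in the exposed group, the relative risk is pulled below 1 and a safety signal could be masked. If it is more complete, a signal could appear where there is none.

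A second, smaller question concerns births at 37 weeks or later. Appendix A asks for a percentile by gestational age, but the curves it names are described only as being for full-term infants.

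**Working it through.** The protocol gives no rate, sample size or power for SGA (Table 1 covers spontaneous abortion and major birth defects), so there is no stated figure to reproduce.

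**Inputs**
- Cut-off: 10th percentile, z = -1.2816 (Appendix A).
- Measures: weight, length, head circumference (Appendix A, section 9.6.2.1).
- Expected exposed live births: 193 × 0.80 = 154 (section 9.5.1).
- Correlation r between the three z-scores: not in the protocol. Assumed equal for all pairs, 0.5 to 0.8, with an outer range of 0 to 0.9.
- Share of infants with all three measures: not in the protocol, assumed.

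**Step 1: expected rate when growth matches the reference**

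P(SGA with k measures) = 1 − P(all k z-scores > −1.2816), under an equicorrelated normal distribution.

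| r | 1 measure | 2 measures | 3 measures |
|---|---|---|---|
| 0 | 10.0% | 19.0% | 27.1% |
| 0.5 | 10.0% | 16.8% | 21.8% |
| 0.7 | 10.0% | 15.3% | 19.0% |
| 0.8 | 10.0% | 14.4% | 17.2% |
| 0.9 | 10.0% | 13.1% | 15.0% |

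The row for r = 0 can be checked by hand: 1 − 0.9³ = 0.271.

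**Step 2: relative risk with identical growth and unequal recording**

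Let f be the share with all three measures, the rest having weight only, and p₃ the three-measure rate. The group rate is f × p₃ + (1 − f) × 0.10.

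At r = 0.5, with f = 0.60 in exposed and 0.90 in comparator infants:
- exposed: 0.60 × 0.2184 + 0.40 × 0.10 = 0.171
- comparator: 0.90 × 0.2184 + 0.10 × 0.10 = 0.207
- relative risk: 0.83

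| Exposed vs comparator with all three | r = 0.5 | r = 0.7 | r = 0.8 |
|---|---|---|---|
| 50% vs 95% | 0.75 | 0.78 | 0.81 |
| 60% vs 90% | 0.83 | 0.85 | 0.87 |
| 90% vs 80% | 1.06 | 1.05 | 1.05 |
| 90% vs 60% | 1.21 | 1.18 | 1.15 |
| equal shares | 1.00 | 1.00 | 1.00 |

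**Step 3: comparison with sampling error**

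Take 154 exposed and 117 × 0.80 ≈ 94 comparator live births. The 80% is the protocol's figure for the exposed group, applied here to the comparators as an assumption. At a 20% rate in both groups, SE(log RR) = √[(0.8/0.2)(1/154 + 1/94)] = 0.262. The 95% limits are then RR × or ÷ exp(1.96 × 0.262) = 1.67. A bias of 0.83 (a factor of 1.21) is smaller than this, but it shifts the whole interval.

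**Step 4: would weight alone be better?**

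Suppose exposure lowers all three measures by 0.5 SD. Approximate power is Φ(log RR / SE − 1.96), with SE² = (1 − p₁)/(154 p₁) + (1 − p₀)/(94 p₀).
- Weight only: 10.0% to 21.7%, log RR 0.776, SE 0.345, power about 61%.
- Composite, r = 0.5: 21.8% to 41.5%, log RR 0.642, SE 0.217, power about 84%.
- Composite, r = 0.8: 17.2% to 33.6%, log RR 0.669, SE 0.253, power about 75%.

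Suppose instead that exposure doubles low weight only (10% to 20%) and leaves the other two measures unchanged. The composite relative risk is then 1.31 (r = 0.5) to 1.37 (r = 0.8), against 2.0 for weight. Neither definition is better throughout.

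**Step 5: composite restricted to complete records**

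With f = 1 in both groups, both rates equal p₃ and the relative risk is 1 when growth is the same, at any r.

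**The case against.** The strongest reply is that a composite applied with equal recording in both groups gives a relative risk of 1 under no effect, and that nothing in the protocol shows unequal recording. That is correct. All three measures are scheduled for every exposed live birth, providers verify them, and the National Coordinator queries missing data. A reader might take the remark in section 9.9, "Because of differences in follow-up procedures across countries and individual reporting patterns", as an admission of uneven measurement. That sentence concerns losses to follow-up, not missing length or head circumference in infants with known outcomes, so it does not support the point. The direction of any bias is equally unknown.

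It can also be said that handling of incomplete measurements may be set out in the statistical analysis plan, which was not available here. Its absence from the protocol is therefore no fault in itself. What stands is that Appendix A fixes the endpoint rule, and that rule makes the rate depend on completeness.

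A reader might also infer that all infants are judged on full-term curves, or that normal infants born at 37 weeks will be over-classified. The documents support neither. Preterm infants are assigned prenatal curves, and the protocol does not show whether the term curves distinguish weeks. Nor does the plan read the SGA rate against 10%, so a composite rate above 10% is not an error by itself.

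Finally, replacing the composite with birth weight alone is tempting. Step 4 shows that this is a trade-off, and the documents do not settle it.

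**Conclusion.** The concern holds in a limited form. As written, the SGA rule makes the expected rate rise with the number of measures recorded: 10% with one and 17-22% with three, for assumed correlations of 0.5-0.8. At every correlation tested, from 0 to 0.9, the three-measure rate exceeds 10%. The planned relative risk is therefore sensitive to any difference in recording between the registry and the comparison cohorts. The size ranges from about 5% for a 90% vs 80% difference to about 13-17% below 1 for 60% vs 90%. The recording shares and correlations are assumptions, and bias is possible rather than demonstrated. SGA is one of several secondary outcomes with no stated power, so this is a modest but worthwhile correction. The term reference remains a query and not a finding.

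**What to change.** In Appendix A:
1. Report weight, length and head circumference at or below the 10th percentile as three separate outcomes, each with its own denominator of infants measured.
2. Keep the any-of-three composite only among infants with all three measures recorded.
3. Apply the same derivation to Cohorts II and III where the patient-level data hold the measurements, and add these to the variable list in section 9.7.4.3 if they can be obtained.
4. As a query, confirm that the reference for births at 37 weeks or later is specific to gestational week. If it is not, use one that is.

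The cost is some wording and programming. No new exposed-group data are needed, because the three measures, gender and gestational age at delivery are already collected. The downsides are a smaller denominator for the composite and dependence on the comparison registry holding birth measurements. Restricting to complete records removes the dependence on the number of measures, but not any selection that arises if recording itself depends on the infant's size or health. The numbers measured should therefore be shown by group.
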